8. CORRELATIVE/SPECIAL STUDIES

8.1 Laboratory Correlative Studies

- Optional biopsies will be frozen and fixed as per SOC protocols in the pathology lab
- Immune response assays
 - o - blood collection, processing and assays will be performed as per the protocols in the Stanford Biobank and Human Immune Monitoring Center where the samples will be stored and assays performed, respectively.
- Others will be sent to relevant reference laboratories

9. STUDY CALENDAR

Visits	Pre Study Visit	Treatment Visits					End of Treatment Visit	Follow Up Visit	Post Study Follow Up
	Wk 0	Wk 1 ^h	Btw Wk 1-3	Wk 4	Wk 7	Wk 10	3 Wks after last dose of Pembrolizumab	Every 3, 6M, or at yr 5 from last dose of Pembrolizumab	Upon progression or unacceptable symptomatology
Investigational Agent ^a		X		X	X	X			
Radiation Therapy ^b			X						
Informed consent	X								
Inclusion/Exclusion Criteria	X								

Demographics	X								
Medical history	X								
Physical Exam	X	X		X	X	X	X	X	
Concurrent meds ^c	X	X		X	X	X	X	X	
Vital signs	X	X		X	X	X	X	X	
ECOG Performance status	X	X		X	X	X	X	X	
ECG	X								
Chest Radiography	X								
Adverse event evaluation		X		X	X	X	X	X	
Tumor measurements	X						X	X	
CBC w/diff	X	X		X	X	X	X	X	
Pregnancy Test ^d (Urine or Serum)	X	X		X	X	X			
Hemoglobin	X	X		X	X	X	X	X	
Hematocrit	X	X		X	X	X	X	X	
Metabolic panel, comp	X	X		X	X	X	X	X	
LDH total serum plasma	X	X		X	X	X	X	X	
Urinalysis Macro (Opt Micro)	X								
TSH w/Reflex FT4 ^e	X						X	X	
Optional Immune Response and Polyomavirus Tests ^f	X		X	X		X	X		
Optional Tumor Biopsy ^f	X		X	X	X	X	X	X	
Survival Follow Up ^g									X

a: Investigational Agent- pembrolizumab 200 mg infused SOC every 3 weeks

b: Radiation Therapy- 1-2 sites of disease, delivered between the first and second cycles of pembrolizumab, 9 Gy X 3 (27 Gy in 3 fractions), or 4-6 Gy X 5 (20-30 Gy in 5 fractions)

c: Concurrent meds will be collected until the patient goes off study due to disease progression or change in therapy for Merkel cell carcinoma or for 2 years of continuing response

d: Pregnancy test conducted and negative result confirmed before administration of pembrolizumab in women with the potential to become pregnant, pregnancy test is required ≤ 6 weeks before first dose of pembrolizumab and optional as clinically indicated for ongoing doses

e: Assessed at week 13 for patients who continue pembrolizumab past week 10

f: If funding is available, a variety of optional immune response assays will be performed that may include Luminex for 51 cytokines testing in serum or plasma, ELISA for MHC class 1 polypeptide-related sequence A (MYCA) and MHC class 1 polypeptide-related sequence B (MYCB) in serum or plasma, immunophenotyping including myeloid-derived suppressor cells (MDSC) and gamma/delta T cells, mass cytometry or CyTOF ICS with phorbol 12-myristate 13-acetate (PMA) + ionomycin stimulation (global immunocompetence assay). These assays will be performed at baseline, 2 weeks (± 1 weeks) and 8 weeks (± 1 weeks) after radiation therapy. Possible tumor biopsies (optional) may be performed before, during/after treatment to assess response to therapy and changes in immune cell subsets. Optional tests to assess polyomavirus in the blood may be performed at baseline and 3 months ± 1 month.

g: Applicable to all subjects who discontinued, regardless of enrollment date. During the Survival Follow-Up Phase, telephone contact will be made every 6 months (± 2 weeks) for 5 years from the last dose of pembrolizumab. The site will inquire about overall subject survival status. Subjects that withdraw from the treatment phase of the study but do not return to the site for any further assessment will be contacted by the site to inquire about AEs and SAEs up to at least 60 days from the last dose of pembrolizumab. Definitely related immune related serious adverse events (irSAEs) will be captured for 6 months after the last dose of study treatment.

h: Required before first dose of pembrolizumab

1. If systemic steroids are required, subjects should be stable on the lowest clinically effective dose (≤ 20 mg/day)

2. Must be at least 14 days since treatment for MCC, and recovered (baseline or residual non ir Grade 1 toxicity or ir Grade 2 toxicity at the investigator's discretion, see section 4.1.1) from any clinically significant toxicity experienced during treatment before the first dose of on study pembrolizumab therapy.
3. ≤ 6 weeks demonstrate measurable disease according to RECIST v1.1, and have baseline (screening/baseline) radiographic images, (e.g. CT, PET CT or MRI brain, chest, abdomen, pelvis, to be determined by the attending physician)
4. ≤ 6 weeks pregnancy test for WOCBP
5. ≤ 1 week labs and liver function tests performed and results evaluated

10. MEASUREMENTS

Title: Tumor response rates (CR, PR, SD, irCR, irPR, irSD) as accessed by RECIST v1.1/irRECIST at both irradiated and unirradiated sites

Time Frame: Response will be accessed at the end of treatment visit and follow up visits

Safety Issue: This outcome is not measuring a safety issue. Safety will be monitored using AE assessment during the trial using the CTCAE v5.0 criteria.

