2.4 Study Design and Duration

This is a single institution, single arm, open-label, Phase II treatment study to evaluate the safety and efficacy of palliative radiation therapy combined with pembrolizumab as a means of providing for PD-1/PD-L1 checkpoint blockade in patients with metastatic Merkel Cell Carcinoma as either first line therapy or upon progression on prior therapy.

In this study, pembrolizumab will be administered at 200 mg IV every 3 weeks as standard of care as approved by the FDA. Palliative radiation therapy will be given between the first and second cycles of immunotherapy.

Subject participation in this study comprises the following time periods:

- Screening
 - Screening assesses the subject's eligibility to participate as determined by the inclusion/exclusion criteria.
 - Screening labs and ECOG Performance Status must be completed within 4 weeks of confirmation of eligibility. Imaging must be completed within 4 weeks of confirmation of eligibility and within 6 weeks of starting pembrolizumab therapy.
 - Eligibility must be confirmed within 28 days of signing the informed consent form.

- Pembrolizumab
 - Patients will receive pembrolizumab as a single agent administered 200 mg as standard of care intravenously every 3 weeks until progression or unacceptable toxicity.
 - Laboratory evaluations must be performed and the results examined before administration of each dose.
 - As durable disease stabilization and/or objective tumor response can be seen after early progression before Week 12, it is recommended that, in the absence of dose-limiting toxicities (e.g., serious AEs), immunotherapy be administered over

the initial 12 weeks even in the setting of apparent clinical progression, providing the subject's performance status remains stable.

- All subjects, including those who may have discontinued treatment for drug-related AEs and/or who have evidence of clinical progression, should obtain a tumor assessment 3 weeks (± 1 week) after the last dose of pembrolizumab.

- Based on clinical experience in ongoing and completed immunotherapy studies, the following recommendations apply for subject management in light of the tumor assessment taken 3 weeks (± 1 week) after the last dose of pembrolizumab:

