- The appearance of new lesions in subjects with other stable or shrinking baseline tumor burden may be experiencing clinical benefit and should continue on treatment before alternative anti-cancer agents are considered. These subjects can be seen to have continued tumor shrinkage in subsequent imaging.
- As long as overall tumor burden is stable or decreasing, subjects can remain in treatment, even in the presence of new lesions, at the discretion of the treating physician.
- Clinical progression warranting alternative anti-cancer treatment should be considered in subjects whose overall tumor burden appears to be substantially increased and/or in subjects whose performance status is decreased.

- Follow-Up

- Subjects with SD, PR or CR will continue receiving pembrolizumab every 3 weeks per standard of care. After the last dose of pembrolizumab, subjects will enter Follow-Up. Efficacy assessments for these subjects are per standard of care.

- Survival Follow-Up (Post Study Follow-Up)

- Subjects who are no longer receiving pembrolizumab due to unacceptable toxicity (e.g., refractory Grade > 3 AEs), disease progression, investigator judgment, or study closure are managed in survival follow-up.

- If possible, subjects will be contacted or medical records reviewed every 6 months (± 2 weeks) for 5 years after the last dose of pembrolizumab to evaluate survival status.

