4. TREATMENT PLAN

Screening/Baseline Visit

The following tests and examinations must be performed and the eligibility criteria satisfied before treatment may begin:

- Histologic diagnosis of Merkel Cell Carcinoma
- Demographics and medical history
- Measurements of weight, height, temperature, pulse, respiratory rate, and resting systolic and diastolic blood pressure
- Complete physical examination
- ECOG Performance Status
- Clinical laboratory tests:
 - Hematology: hemoglobin, hematocrit, CBC counts with differential (including absolute lymphocyte count) and direct platelet count
 - Serum Chemistry: albumin, serum alkaline phosphatase, SGOT (AST)/SGPT (ALT), total bilirubin, calcium, creatinine, glucose, lactate dehydrogenase (LDH), total protein, urea nitrogen (BUN), electrolytes (including sodium, potassium, chloride, and bicarbonate), TSH w/Reflex FT4
 - Urinalysis:
 - Gross examination including specific gravity, protein, glucose, and blood
 - Optional microscopic examination including WBC/HPF, RBC/HPF and any additional findings
- Optional Blood sample obtained for investigational immune response assays
- Chest radiography unless baseline CT scan was performed
- Electrocardiogram
- Relevant baseline radiographic images (e.g. brain, chest, abdomen, pelvis, and bone scans with the exact imaging studies utilized determined by the attending physician) within 6 weeks of initiation of anti-PD-1/PD-L1

- Current medications
- Baseline review of symptoms
- Pregnancy test
- Optional Tumor biopsy

Treatment Visits

The day subjects receive the first dose of pembrolizumab therapy will define Day 1. Subjects are required to have blood collected and chemistry labs analyzed up to 1 week prior to each dose of pembrolizumab. Investigators or an assigned medical professional must review liver function tests from the predosing labs and ensure the results meet dosing requirements prior to authorizing administration of each dose of pembrolizumab.

Subjects will receive a single dose of pembrolizumab as standard of care with 200mg IV every 3 weeks (with a -3 and +7-days window) until disease progression or unacceptable toxicity occurs.

During this treatment phase, the following procedures will be performed within 1 week of each scheduled visit:

- Pregnancy test for WOCBP, required within 6 weeks before first dose of pembrolizumab, then optional as clinically indicated for ongoing doses

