- Vital sign measurements will include weight, temperature, pulse, and resting systolic and diastolic blood pressure. Vital sign measurements of pulse, and systolic and diastolic blood pressure will be collected prior to the infusion of anti-PD-1/PD-L1.
- Physical examination
- ECOG Performance Status
- Clinical laboratory tests (as outlined in the screening phase) (taken and results reviewed prior to study drug administration):
 - Hematology
 - Serum chemistry
 - TSH w/Reflex FT4- week 13 only (for patients who continue pembrolizumab past week 10)
- Blood (optional) for investigational immune response assays at 2 weeks (± 1 weeks) and 8 weeks (± 1 weeks) after completion of radiation therapy.
- Concomitant medications
- Adverse event assessment
- Optional Tumor biopsy

Follow-up

Patients will be seen for an end of treatment visit 3 weeks (± 1 week) after the last pembrolizumab dose and again for follow up visits every 3 months (± 1 month) for 2 years and then every 6 months (± 1 month) for years 3-4 and again at year 5 (± 1 month) per SOC thereafter until progression of disease by imaging criteria or increased symptomatology that requires another therapy. Follow up visits will be performed until 5 years from the last dose of pembrolizumab and will then become optional and SOC.

The following procedures will be performed at each scheduled follow-up visit ± 1 month during the first 2 years. During years 3-5 the clinical laboratory tests will be performed only once per year.

- Measurements of vital signs (resting systolic and diastolic blood pressure, pulse, respiratory rate, and temperature) and weight
- Physical examination
- ECOG Performance Status
- Clinical laboratory tests
 - Hematology
 - Serum chemistry
 - TSH w/Reflex FT4

- Concomitant medications (for the first 2 years)
- Adverse event assessment (for the first 2 years)
- Status of new and continuing AEs and SAEs (at minimum, collected up to 60 days following last dose of pembrolizumab, 6 months for irSAEs definitely related)
- Relevant imaging studies for tumor measurements
- Optional Tumor biopsy

Survival Follow-Up Assessment for all Subjects

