10.1.4 Measurement Time Points

Tumor measurements will be taken and RECIST v1.1/irRECIST will be calculated from the scans (CT, PET CT or MRI brain, chest, abdomen, pelvis, to be determined by the attending physician) performed at baseline, end of treatment visit, and follow up visits.

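### Scored scans are dated from the last pembrolizumab dose, so on two of three readings of the schedule a RECIST response cannot be confirmed in a patient dosed to imaging progression

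*Combined protocol and SAP*

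**What the plan says.** **Scored time points.** Section 10 states that "Response will be accessed at the end of treatment visit and follow up visits". Section 10.1.4 takes the measurements from scans "performed at baseline, end of treatment visit, and follow up visits". Section 10.1 puts follow-up imaging at 3-month intervals or shorter (± 1 month) for two years, then less often, counted from the last dose.

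**Calendar (section 9).** Tumour measurements are marked at the pre-study, end-of-treatment and follow-up columns, and in none of the week 1 to week 10 treatment columns. End of treatment is dated 3 weeks after the last dose. The follow-up column is headed "Every 3, 6M, or at yr 5 from last dose of Pembrolizumab".

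**Procedure lists (section 4).** The treatment-visit list, introduced by "the following procedures will be performed within 1 week of each scheduled visit", contains no imaging. It does add a thyroid test at "week 13 only (for patients who continue pembrolizumab past week 10"). After baseline, "Relevant imaging studies for tumor measurements" appears only in the follow-up list.

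**Dosing.** Section 2.4 gives pembrolizumab "intravenously every 3 weeks until progression or unacceptable toxicity". Patients with SD, PR or CR stay on drug. It then says: "After the last dose of pembrolizumab, subjects will enter Follow-Up". Efficacy assessment for these patients is left to standard of care, with no interval and no statement that the scans are scored. The synopsis describes treatment length in two further ways: four cycles or until progression or toxicity, and at least four cycles.

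**Response rules.** Best response runs from the start of treatment to progression (10.1.2.4). CR and PR need confirmation at least 4 weeks later (10.1.2.5). After progression the patient moves to survival follow-up, for which the calendar marks no tumour measurements.

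**The concern.** The endpoint needs two scored scans at least 4 weeks apart before progression. The schedule dates its post-baseline scans from the end of dosing, and responders are the patients kept on drug. Someone treated until imaging shows progression may therefore reach progression with too few scheduled scored scans to register a confirmed response, while someone with the same tumour course who stopped for toxicity has enough.

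At stake are the confirmed CR rate (the primary endpoint in 12.3), the confirmed response rate and duration of response (12.4), and the nadir against which PD is judged (10.1.2.3). If sites choose for themselves whether to score standard-of-care scans, the endpoint also depends on that choice.

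**Working it through.** The plan gives no figure for this point, so the check is a timeline. The precision figures in 12.5 are not at issue.

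**Inputs.** Doses every 3 weeks from week 1 (calendar). End-of-treatment visit 3 ± 1 weeks after the last dose (section 4, calendar). First follow-up scan 3 ± 1 months after the last dose (10.1, calendar). Confirmation at 4 weeks or more (10.1.2.5). One month = 365.25/12/7 = 4.348 weeks.

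**Step 1: patients who stop without progression.** Gap between the end-of-treatment scan and the first follow-up scan:
- minimum 2 × 4.348 − 4 = 4.7 weeks
- nominal 3 × 4.348 − 3 = 10.0 weeks
- maximum 4 × 4.348 − 2 = 15.4 weeks

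Every value exceeds 4 weeks, so confirmation is possible.

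**Step 2: patients dosed to imaging progression.** Dose k falls at week 1 + 3(k − 1). For 4, 8 or 17 cycles the last dose is at week 10, 22 or 49, and a scan 3 weeks later is at week 13, 25 or 52. Three readings of the schedule:

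| Reading | Scheduled scored scans before progression | RECIST CR/PR confirmable? |
|---|---|---|
| A. End-of-treatment visit follows the final dose | 0; the first scan falls at or after progression | No |
| B. End-of-treatment visit at about week 13; follow-up still from the actual last dose | 1; the next is 12 weeks later (8 cycles) or 39 weeks later (17 cycles), at or after progression | No |
| C. End-of-treatment visit at about week 13; 3-monthly scans run from there during dosing | 2 or more, if progression comes after the second | Yes |

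On reading C the second scan is at about week 10 + 13.0 = 23 if counted from the fourth dose, or 13 + 13.0 = 26 if counted from the week-13 visit. Either is more than 4 weeks after the first.

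**Step 3: effect on scoring.** Take illustrative target-lesion sums of 100 mm at baseline, 50 mm at week 13 and 65 mm after the last dose, with no new lesions.
- Reading B: 65 against the nadir of 50 is +30% (+15 mm), so PD. The table in 10.1.2.5 codes PR-then-PD as SD if a minimum SD duration is met (the documents do not state one), otherwise PD.
- Reading A: the 50 mm scan is not scored, so baseline is the smallest sum. 65 against 100 is −35%, an unconfirmed PR recorded when the tumour had already regrown.

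**Step 4: timing, illustration only.** The single-agent pembrolizumab trial cited in section 2.2 had a median time to response of 2.8 months. Of its 28 responders, 96% had a duration of at least 6 months and 54% of 12 months or more. Assume those times apply here and the last dose falls at progression. The reading A scan is then at 2.8 + 6 + 0.69 = 9.5 months or 2.8 + 12 + 0.69 = 15.5 months, after the response has ended. On reading B the gap after the week-13 scan (12 weeks from day 1, 2.76 months) is 6.7 or 12.7 months.

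**The case against.** **The schedule can be read so that confirmation works.** A reader might infer that no interpretation allows a confirmed response. That goes too far. Section 10.1 places scans at end of treatment and then 3-monthly. Section 2.4 describes continued dosing of SD, PR and CR patients under its Follow-Up heading. The calendar's dosing columns end at week 10. The thyroid test assigned to week 13 for continuing patients is marked, after baseline, only in the two columns that also carry tumour measurements. All of this fits reading C. Against it, section 2.4 says "After the last dose of pembrolizumab, subjects will enter Follow-Up", and the calendar header and 10.1 count from the last dose. These weigh against reading C without excluding it.

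**Reading A fits parts of the text poorly.** Section 4.2 makes progression at or after the end-of-treatment visit a reason to stop, and 2.4 lets patients continue after that assessment. Both imply a visit during treatment. This stands, and it limits the weight of the 9.5 and 15.5 month figures. Section 4 and the calendar still date the visit from the last dose.

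**On-treatment scans may already count.** Best response runs from the start of treatment, the follow-up interval in 10.1 is a maximum, and 10.1.4 does not say that other scans are excluded. So it cannot be said that on-treatment responses are never scored. What remains is that nothing requires them to be scored and no interval is set.

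**Not every endpoint is hit equally.** Section 10.1.3 states no confirmation rule for irCR or irPR, so on reading B a week-13 irPR stands. The rate in section 1.1 counts SD, so a PR-then-PD patient recoded as SD would still count there if the minimum duration is met.

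**Futility.** A reader might infer that the chance of a futility stop is raised by a definite amount. Section 12.2 does not say that responses must be confirmed or which scans count. At a 20% rate, P(1 or fewer of 15) = 0.8^15 + 15 × 0.2 × 0.8^14 = 16.7%, which is a property of the rule whatever the scan timing. Any higher figure needs an assumed share of missed responses.

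**Conclusion.** The point holds as a defect of the schedule as written, with moderate confidence, and it should be fixed. For a patient dosed to imaging progression, scheduled scored scans before progression number 0 on reading A and 1 on reading B, where confirmation needs 2. Only reading C supplies them. Patients who stop without progression get two usable scans, so classification can depend on the reason for stopping.

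The effect falls on confirmed RECIST 1.1 CR and PR, nadir and duration of response. It is smaller for irCR and irPR and for the rate that counts SD. The conclusion concerns scheduled scans only. It rests on section 10.1.2.5 applying to the response endpoints, as its own wording says, and on standard-of-care scans not being scored, on which the plan is silent. Neither the share of responses affected nor any effect on the futility count can be derived from the documents.

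**What to change.** **Core change, in 10, 10.1, 10.1.4 and the calendar.** State that all tumour imaging from the first dose, including standard-of-care scans during treatment, is scored by RECIST v1.1 until RECIST PD and by irRECIST until confirmed irPD. Say that this includes scans taken to confirm irPD and scans after early progression while treatment continues; a plain cut-off at progression would lose both. State that these scans count toward best overall response, confirmation, nadir and duration of response.

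**Definitions.** Define the end-of-treatment assessment and say when the 3-monthly interval starts. In 12.2, state which scans enter the count and whether responses must be confirmed.

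**Reconciliation.** The sponsor must reconcile the synopsis, 2.4, 4, 4.2, 5.1.1.3, 9 and 10.1 on treatment length and the end-of-treatment visit. No treatment duration or clinical rule is proposed here.

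**Optional.** Time scored assessments from the first dose whether or not dosing continues. With the core change alone, scan timing still varies between patients.

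**Cost.** The core change is protocol and calendar wording plus scoring of scans already taken. The optional change may need some extra scans if standard-of-care imaging is less frequent than 3-monthly; the documents give no standard-of-care interval.

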10.1 Primary and Secondary Outcome measures

The primary and secondary outcomes will be assessed by obtaining relevant tumor images at baseline line, end of treatment visit, and then at least every 3 months (± 1 month) for two years and then every 6 months (± 1 month) for years 3-4, then again at year 5 (± 1 month) from the last dose of pembrolizumab or until disease progression. Response and progression will be evaluated using the new international criteria proposed by the revised Response Evaluation Criteria in Solid Tumors (RECIST) guideline (version 1.1)¹¹ as well as the Immune-related RECIST (irRECIST).¹² Changes in the largest diameter (unidimensional measurement) of the tumor lesions and the shortest diameter in the case of malignant lymph nodes are used in the RECIST criteria. RECIST/irRECIST criteria will be used to score response of both the irradiated and unirradiated disease sites.

